For all specific aims:

Prior to conducting any research related tests / procedures, the patient will be consented. The consent process will be facilitated by the IRB approved research coordinator and will occur in a private room in the pre-operative area prior to surgery. Once in the operating suite, the patient will be put under anesthesia for clinical purposes for surgery. Privacy will be maintained by limiting the individuals in the operating room to only necessary IRB approved research personnel. In addition, all data collected during the study will be immediately de-identified and stored on an encrypted, password protected server.

Behavioral Assessments. For each experiment, three behavioral responses will be evaluated: (1) loss/recovery of spontaneous movement (i.e., loss and recovery of responsiveness (LOR/ROR)) (2) loss/recovery of movement in response to stimuli (separately to clicks [non-salient] and verbal stimuli [salient], as per prior work by Purdon and colleagues⁴), and (3) loss/recovery of movement to command (verbal command with patient name with instruction to show different numbers of fingers, as proxy of loss/recovery of consciousness (LOC/ROC)). Stimuli will be presented in an interleaved fashion every 4 seconds binaurally via headphones (15 presentations of each stimuli at each dose, total 5 min per dose, or until failure to respond 3 times in a row to a certain stimulus). We use these separate measures because of the literature and our hypothesis that circuits mediating responsiveness and consciousness are separable. Namely, numerous studies highlight that consciousness (defined as ability to interact with the environment, most often measured by the isolated forearm test) can be maintained even with loss of responsiveness.^{39, 56}

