The patient will emerge from anesthesia for clinical placement of the left DBS electrode and neurological testing done by [name] and the neurologist. Once clinical testing is complete, the ECoG strip will be placed on the right side for research purposes. Then, [name] will continue with the clinical procedure and place the right DBS electrode and conduct neurological testing to confirm placement. The researchers will connect ECoG and DBS leads to the Neuro-Omega system to record brain signals throughout research related tasks. Once all clinical testing has been completed, the research team will simultaneously record cortical ECoG and pallidal LFP from GPI/GPe during both induction and emergence with target-controlled infusion of propofol detailed above. During induction and emergence, the participant will also complete the behavioral task detailed above. If data is being collected for **Specific Aim 2**, ECoG /LFP recordings and behavioral assessments will take place with no stimulation. If data is being collected for **Specific Aim 3b**, recordings and behavioral assessments will be made during both induction and emergence of anesthesia with either GPI or GPe stimulation. When the research portion is complete, the ECoG strips will be removed and the surgery will finish per clinical standard of care.

DATA ANALYSIS

LFP Analyses:

Signal analysis is performed in MATLAB (The Mathworks Inc., Natick, MA). Data is parsed into various behavioral and stimulation state epochs, excluding any sections containing electrical or movement artifact using methods previously described.^{41, 50} Bipolar re-referencing of adjacent contacts is used in order to emphasize local and minimize global signals, which is critical for the proposed network coupling analyses across brain regions. 60 Hz line noise is rejected using a notch filter. 60 Hz line noise is rejected using a notch filter.

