Measures of Network Coupling (bivariate, assessed over time and trials) In our approach, when we refer to analyzing "network coupling," we will investigate a broad range of coupling measures. The measures and their rationale are summarized here. Coherence, the most commonly used measure of LFP coupling, is used to describe the degree of co-variability between signal pairs over different frequency ranges.⁶¹ To find the time-frequency representation of coherence for pairs of signals, we use a moving window approach and multi-taper method. Phase synchrony index, a measure of consistency of phase differences between two signals, is used to separately evaluate the specific role of phase difference on neurophysiological observations. Phase locking is of particular interest as fixed phase relationships may be particularly detrimental to information transfer across nodes.⁶² Phase-Amplitude Coupling (PAC) is assessed both locally and across nodes and across time and across trials and is quantified using modulation index (MI).⁶³ PAC is a critical measure that has been identified as a putative pathophysiological mechanism and our group has previously shown to be a potential mechanism for long distance coordination of physiological signals.¹⁶ MI is a method based on Kullback-Liebler (KL) divergence used to extract PAC, described previously. In order to extract the phase from phase signals corresponding to the peak of amplitude signal which we refer to as preferred phase, the weights of the phaseamplitude histogram were used as amplitudes of a vector, while the center phase of each bin constituted the phase of the vector. Statistical significance of MI values is evaluated using surrogate data analysis (by circularly shifting one series relative to the other). MI values are then converted into z-scores and false discovery rate (FDR) is used to correct p-values for multiple comparisons.⁶⁴ Phase lag index (PLI) is used to determine if one signal consistently leads or lags another signal, using non-zero iCoh which indicates an interaction between signals that cannot be due to volume conduction. PLI measures the

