extent to which a distribution of phase angle differences is distributed toward the positive or negative side of the imaginary axis on the complex plane. Specifically, we employ unbiased weighted PLI⁶² in which angle differences are weighted according to their distance from the real axis. We emulate the moving window approach used in the spectral analyses described above, allowing evaluation of patterns of changes in these measures over time. Phase slope index is also used as a measure of the consistency of directional flow within a frequency by determining if the slope of the phase lag between two processes is positive or negative over several adjacent frequency bins, suggesting the direction of signal flow. To assess directionality of the changes, we will perform multivariate granger causality analysis⁶⁵ Similar to the power, connectivity analysis will be performed both across the time^{16, 41-43, 50, 66} and the trials⁶⁷ and with frequency and time resolution similar to the spectral analysis.

Graph theory is used to characterize global network architecture and the inter-relatedness of the nodes.⁶⁸ We will employ weighted connectivity measures to construct functional network diagrams and extract metrics using the Brain Connectivity Toolbox.⁶⁹ Given only 5 nodes, we will compare the following measures across conditions: node degree, clustering, pathlengths, and identification of hubs. Dynamic Causal Modeling (DCM), implemented in SPM70, is used to evaluate causal network architecture rather than separately evaluating pairs of nodes. DCM identifies the most likely among a set of competing models that best accounts for observed neural dynamics, allowing modeling of missing nodes which is critical since human studies preclude evaluation of every node.

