Statistical Analysis is done using SPSS. We assess the significance of connectivity measures by shuffling data to create a permutation distribution and calculating Monte-Carlo estimates of the significance probabilities and/or critical values using parametric/nonparametric statistical tests. We will explore the correlation between behavioral and LFP metrics, and clinical scores (total and lateralized UPDRS-III) using a multiple linear regression model. To confirm generalization to new data points, a "leave one-out" procedure will be employed and finally a coefficient of determination (R²) and RMS of errors will be calculated for all generalization data. T-tests will be used to compare between conditions. To investigate interactions, two factor ANOVA will be used. Gaussian "v-test" and Rayleigh tests will be used to compare the preferred phase angle of connectivity with the uniform distribution to infer phase specificity.⁷¹ The Watson-Williams two-sample test (i.e. circular analogue of the two-sample t-test) will be used to assess whether the mean directions of two groups are identical.

Specific Aim 1:

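### Across-trial coupling is not separated from responses to the sounds played every 4 s, so a shared sound response can pass for coupling and a fading one for a change in coupling

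*Combined protocol and SAP*

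**What the plan says.** All references are to section 4.a of the combined protocol and SAP.

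- **Sounds.** Behavioral Assessments: "Stimuli will be presented in an interleaved fashion every 4 seconds binaurally via headphones". The number is given as "15 presentations of each stimuli at each dose, total 5 min per dose, or until failure to respond 3 times in a row".
- **Recording during the sounds.** The surgical timeline for Aims 2 and 3b has cortical ECoG and pallidal LFP recorded through induction and emergence, and adds: "During induction and emergence, the participant will also complete the behavioral task detailed above".
- **Coupling across trials.** The section is headed "Measures of Network Coupling (bivariate, assessed over time and trials". Phase-amplitude coupling (PAC) is "assessed both locally and across nodes and across time and across trials and is quantified using modulation index (MI". The section later says that "connectivity analysis will be performed both across the time" and across trials.
- **Null for MI.** "Statistical significance of MI values is evaluated using surrogate data analysis (by circularly shifting one series relative to the other".
- **Null for connectivity in general.** The Statistical Analysis paragraph says: "We assess the significance of connectivity measures by shuffling data to create a permutation distribution". It does not say whether samples, epochs, trials or condition labels are shuffled. The same paragraph plans t-tests between conditions and does not say that the compared values are corrected by surrogates.
- **Preprocessing.** LFP Analyses lists artifact exclusion, bipolar re-referencing, a 60 Hz notch filter and several steps against the DBS pulse. None concerns responses to sound.

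The term trials is not defined. LFP Analyses also uses it for periods of DBS.

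**The concern.** A sound heard through headphones is a common input. If two recorded nodes each respond to it with a fairly fixed latency, their phases, and the phase of one and the amplitude of the other, line up from presentation to presentation even though neither node influences the other. An across-trial measure counts that alignment as coupling.

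A circular shift moves one series in time against the other. In the surrogates the two responses no longer coincide, while in the real data they do. The real value is therefore compared with a null from which the shared response has been removed, and can exceed it with no interaction present.

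The second problem is the comparison of states. Aim 2 relates behavioral loss of responsiveness and consciousness to changes in pallidocortical circuits, and Aim 3b uses the same techniques. If the sound response becomes smaller as the patient stops responding, the false part of the coupling falls at the same moment as the behavioral endpoint. This needs no movement and no imbalance in trial numbers, and an unbiased estimator does not remove it.

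**Working it through.** The plan gives no figure on this point, so the check is by simulation.

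**Inputs from the plan.** Sounds every 4 s; 15 presentations per type; three types (clicks, verbal stimuli, command), so 15 or 3 × 15 = 45 trials per dose. (3 × 15 × 4 s = 3 min, not the stated 5 min, so the trial count itself needs clarifying.) For comparisons between states, 16 patients as in Aim 2. That number reproduces: a two-sided one-sample t-test with d = 0.75 and n = 16 has power 0.801, and 16/0.8 = 20. It is not in dispute.

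**Assumed inputs.** The size of the sound response in each node, awake or under propofol, is not given. Peaks of 0, 0.5, 1 and 2 background SD were used.

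**Step 1: one state, no true coupling.** Two independent 1/f-noise nodes each receive a 6 Hz response locked to the sound (latencies 200 and 250 ms, 30% gain variation between trials); one also receives a sound-locked 30–60 Hz burst. Phase locking is PLV = |(1/K) Σ exp(i(φA − φB))| over K trials, taken at one time point just after the sound. MI uses theta phase and 30–60 Hz amplitude. There were 120 datasets per case and 99 surrogates. At a true 5% the Monte Carlo standard error is √(0.05 × 0.95/120) = 2.0 points.

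Sanity check: with no response, expected PLV is about √π/(2√K), which is 0.23 for K = 15 and 0.13 for K = 45. The simulation gave 0.22 and 0.12.

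False-positive rate (%) with the circular-shift null and no evoked subtraction:

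| Measure, trials | 0 SD | 0.5 SD | 1 SD | 2 SD |
|---|---|---|---|---|
| MI, continuous series, 15 | 6 | 8 | 7 | 20 |
| MI, continuous series, 45 | 6 | 11 | 12 | 33 |
| MI, post-sound window, 15 | 5 | 5 | 14 | 45 |
| MI, post-sound window, 45 | 6 | 7 | 36 | 46 |
| PLV, 15 | 1 | 21 | 66 | 79 |
| PLV, 45 | 6 | 59 | 84 | 92 |

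The PLV rows show what would happen if the circular shift were used there; the plan names it only for MI. With responses of 0.5–2 SD and a trial-shuffled null, PLV and post-sound MI both gave 4–7%. With the mean evoked response subtracted and the circular shift kept, PLV gave 5–7% and post-sound MI 3–8%.

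**Step 2: change of state, no true coupling.** If the response fades from 1 SD to 0, mean PLV falls from 0.69 to 0.22 (15 trials) or from 0.68 to 0.12 (45 trials). False state differences by paired t-test on uncorrected values, 16 patients, 15 trials per state, 150 replicates:

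| Measure | 0.5 SD when responsive | 1 SD when responsive |
|---|---|---|
| Unbiased theta phase consistency after the sound (separate simulations) | 39–40%, 26–29%, 17–25% | 100% |
| Debiased weighted PLI, latencies 50 ms apart | 37–45% | 100% |
| 1 s multitaper windows, sound-locked | 5–8% | 97–100% |
| 1 s multitaper windows, pooled over the state epoch | 5–8% | 15–24% |

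In the first two rows the response fell to 0–0.25 SD (left column) or 0–0.5 SD (right column). Beta-band coupling stayed at 2–7%, as expected with a 6 Hz response. With no evoked response the rate was 5%. Subtracting the mean evoked response brought it to 1–7%, and subtracting the trial-shuffled value to 3–7%.

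**Why weighted PLI does not help.** It discounts zero-lag mixing. At 6 Hz a 50 ms latency difference is 0.05 × 6 × 360° = 108°, which is read as a genuine lag.

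**The case against.** The strongest reply has five parts.

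- **A second null exists.** A reader might infer that the circular shift is the plan's only surrogate and that all coupling results fall with it. The documents do not support that. The circular shift is tied to MI, where the simulated inflation is smaller. The other measures are tested by shuffling, and if trials are shuffled, significance within a state is protected (4–7%). This stands. What remains is that the unit is unstated and that the t-tests between conditions are not said to use corrected values. Permuting state labels would not help, because the evoked response itself differs between states.
- **Trials may not be sound presentations.** The plan parses data by behavioral and stimulation state. If windows are pooled over a state, the effect at 1 SD falls to 15–24%, and MI over the continuous series stays at 6–12%. This stands. Sound presentations are nonetheless the repeated events in this task, so a definition is owed.
- **The evoked response is assumed.** A reader might infer that the trial will report decoupling at loss of consciousness when none occurred. The documents give neither a response size in these nodes nor its decline under propofol. The risk is conditional.
- **Data are not raw.** A reader might infer that coupling is computed on unprocessed epochs. It is not, but none of the listed steps addresses sound-locked activity.
- **Aim 2 does not name breakdown of coupling as its conclusion.** It plans to correlate behavior with circuit changes, its sample size rests on alpha/beta power, and the plan itself says that fixed phase relations may hinder information transfer. The claim that the main Aim 2 conclusion is invalid therefore goes too far. The across-trial coupling results are what is exposed.

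**Conclusion.** The concern holds as an omission with a conditional consequence. The plan has no step that separates sound-locked activity from ongoing coupling, the null named for MI does not control for it, and the null for other across-trial measures is not specified well enough to tell. Uncorrected values compared between states are exposed whichever null is used within a state.

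The size rests on three things that the plan does not state: the evoked amplitude in both nodes, the frequency band, and whether windows are locked to the sounds. The effect ranges from little or none (no response, a band that the response does not reach, or MI over the continuous series up to about 1 SD) to near-certain false state differences for theta phase measures in sound-locked windows at 1 SD. A false change between states also requires that the response shrink with responsiveness, which is an assumption. The change is worth making before analysis, because the confound would move in step with the behavioral endpoint.

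**What to change.** 1. Define trials for the across-trial measures, and say which windows are locked to the sounds.
2. For sound-locked epochs, replace the circular shift with trial-shuffled surrogates: take one node's phase from one presentation and the other node's phase or amplitude from another of the same stimulus type and state. Stimulus locking then stays in the null.
3. In the Statistical Analysis paragraph, name trial shuffling as the null for all across-trial measures, including weighted PLI.
4. Compare surrogate-corrected values, not raw ones, between states and between stimulation conditions.
5. Report across-trial coupling also with the mean evoked response subtracted per channel, stimulus type and state. Treat this as a paired check, not a substitute, because subtraction leaves trial-to-trial variation in response size.

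This needs no new data and no change in procedure. The cost is noisier estimates where the three-failure stop leaves few presentations. Those steps should be pooled or flagged rather than dropped automatically, since they may lie close to loss of response, which is the period that Aim 2 studies.

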In Specific Aim 1, we aim to demonstrate differences in propofol sensitivity across 2 patient cohorts based on the presence of absence of basal ganglia pathology (Parkinson disease [PD] and essential tremor, respectively). By characterizing and demonstrating differences in group level pharmacokinetic/pharmacodynamics of propofol (primary endpoints), we will provide evidence suggesting basal ganglia pathology is associated with differential response to propofol suggesting the basal ganglia are an important part of brain circuitry regulating consciousness. This aim will be completed entirely at UCLA.

In Specific Aim 2, we aim to characterize the temporal evolution of brain signals (recorded from the cortex and the basal ganglia) with propofol induced loss and recovery of consciousness to identify network level changes correlating with consciousness. All subjects will have PD and will be assigned to the same intervention of propofol administration and withdrawal, while we invasively record brain signals from key nodes in the hypothesized brain networks regulating consciousness. The primary endpoint/outcome will be neurophysiologic data.

In Specific Aim 3A, we aim to demonstrate the role of the basal ganglia in regulating consciousness by focally modulating the network with deep brain stimulation (DBS). Patient with PD and previously implanted DBS will be randomly assigned to undergo anesthetic induction either with or without DBS. Primary endpoint will be the characterization of the pharmacokinetics/pharmacodynamics with and without stimulation with PD. We expect to see shifts in the kinetics and dynamics associated with DBS, suggesting focal modulation of the circuit alters consciousness regulating circuitry of the brain.

In Specific Aim 3B, we will conduct a final clinical trial in which we will, as in Aim 3, record from the brain of patients undergoing DBS implantation, now with or without DBS on during both induction and emergence from propofol anesthesia. The primary outcome will be neurophysiological signals and observing perturbations of the evolution of the brain signals with vs without DBS.

2. Background.

- Describe past experimental and/or clinical findings leading to the formulation of your study.
- For research involving investigational drugs, describe the previously conducted animal and human studies.
- For research that involves FDA approved drugs or devices, describe the FDA approved uses of this drug/device in relation to your protocol.

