Aim 1: We estimate our sample size using a Monte Carlo simulation based on predicted differences in propofol sensitivity as defined in prior studies,^{47, 48, 57, 75} which suggest a 20% difference in Ce50 with 20% intersubject variability and an additive measurement error. We performed the Monte Carlo simulation by constructing two population response curves from N patients whose response to propofol was determined by the sigmoidal Emax model while varying only the Ce50 between the populations. The nonlinear fitting was performed for both populations and this process was repeated 1000 times, with the fraction correctly identifying the underlying difference in the model used as our power estimate. N was then incremented until 80% power was obtained, which required approximately 24 patients per arm (total of 48 patients). Similar studies have targeted enrollments of 18-31 subjects per arm.^{47, 48, 76} To account for an estimated 20% dropout rate or protocol error, we plan to recruit a total of 58 subjects. All patients will be recruited from / data collection will occur at UCLA for Specific Aim 1.

Aim 2: Our experiments are purposefully designed to ensure proper power and that experiments can be completed within intraoperative time constraints. Using our prior LFP recordings in PD as well as the published literature^{43, 78, 79}, we conducted a power analysis based on average α/β power modulation between rest and anesthetized state observation (Figure 1). Power analysis indicates a total of 16 patients is required to achieve significant results (one-sample t-test with $d=0.75$, $p=0.8$, $\alpha=0.05$). To account for an estimated 20% dropout rate or protocol error, we plan to recruit at least 20 subjects. Data collection will occur at UTSW and UCLA.

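### Aims 2 and 3b name no specific primary measure, and multiplicity control is stated only for modulation-index values, so familywise error is uncontrolled

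*Combined protocol and SAP*

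**What the plan says.** **Primary outcomes.** Section 1 (Purpose and objectives) says for Aim 2: "The primary endpoint/outcome will be neurophysiologic data". For Aim 3b it says: "The primary outcome will be neurophysiological signals and observing perturbations of the evolution of the brain signals with vs without DBS". Neither statement gives a measure, recording site, node pair, frequency band, time window or contrast. The Aim 2 and Aim 3b entries under Data Analysis in section 4.a refer back to the LFP analyses and set no order of importance.

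**Breadth.** Under Measures of Network Coupling the investigators write that "we will investigate a broad range of coupling measures". Six are described: coherence, phase synchrony index, phase-amplitude coupling (by MI), weighted phase lag index, phase slope index and Granger causality. Graph metrics follow ("Given only 5 nodes, we will compare the following measures across conditions: node degree, clustering, pathlengths, and identification of hubs"), then dynamic causal modelling. Connectivity is analysed over both time and trials, "and with frequency and time resolution similar to the spectral analysis".

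**Multiplicity.** FDR appears once, directly after the surrogate-data test of MI values: "false discovery rate (FDR) is used to correct p-values for multiple comparisons". No level and no family are given. The Statistical Analysis paragraph assesses connectivity measures against a permutation distribution, using Monte-Carlo significance probabilities, critical values or both. It then says: "T-tests will be used to compare between conditions". ANOVA is planned for interactions and circular tests for phase angles. No adjustment is stated for any of these.

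**Sample size.** Aims 2 and 3b share one calculation, on average alpha/beta "power modulation between rest and anesthetized state observation". It is a one-sample t-test with d = 0.75, power 0.8 and alpha 0.05, giving 16 patients, with at least 20 recruited.

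**The concern.** The 80% power and 5% alpha belong to one test of one quantity, and the plan never declares that quantity to be the outcome. The declared outcome is in effect the whole recording, open to many measures, pairs, bands, windows and states. If each contrast is read at an unadjusted 5%, some may reach significance by chance, and nothing in the plan separates the result the study was sized for from the others. At stake is whether a reported network correlate of consciousness (Aim 2) or stimulation effect (Aim 3b) carries the error rate that a reader would assume from the stated alpha.

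**Working it through.** **1. The plan's own figure.** Inputs from Sample Size, Aims 2 and 3b: d = 0.75, alpha 0.05, power 0.8, one-sample t-test. For n = 16 the noncentrality is 0.75 × √16 = 3.0 on 15 df. Two-sided exact power is 0.801, and 16 is the smallest n that reaches 0.8. A one-sided test would need only 13, so the plan's 16 matches a two-sided test. Dropout: 16 / 0.8 = 20. The figure reproduces, and it supports one test.

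**2. An illustrative count of tests.** The plan gives no count.
- Nodes: 5 (graph-theory paragraph), so 5 × 4 / 2 = 10 undirected pairs.
- Coupling measures: 6 described. MI has a stated FDR step, so it is left out: 5.
- One test per measure and pair: 5 × 10 = 50.

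This leaves out any multiplication by band, window or state, and it omits the graph metrics and causal models. It treats Granger causality as one test per pair, although the plan calls it multivariate.

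**3. Error rates at an unadjusted 5%, all nulls true.**
- Expected false positives: 0.05 × 50 = 2.5, whatever the correlation.
- Chance of at least one if independent: 1 − 0.95^50 = 0.923.
- Under dependence: simulated equicorrelated one-sample t-tests with n = 16.

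| Tests | Basis | Expected false positives | Chance of any, correlation 0 | 0.5 | 0.8 |
|---|---|---|---|---|---|
| 10 | one measure, 10 pairs | 0.5 | 40% | 31% | 18% |
| 50 | five non-MI measures, 10 pairs | 2.5 | 92% | 65% | 32% |
| 300 | six measures, 10 pairs, five bands (assumed) | 15 | >99.9% | 94% | 51% |

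The simulated entries are good to about two percentage points, so 64% and 30% for 50 tests would serve equally well. The last row includes MI and assumes a number of bands, so it only shows the direction.

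**4. What 16 patients can carry.** With a Bonferroni correction at d = 0.75, power at n = 16 falls from 80% for one test to 42% for 10 tests and 21% for 50.

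**5. Aim 3b.** Section 3 and the Aim 3b analysis paragraph compare stimulated patients with the unstimulated patients of Aim 2. These are different people, so the test is two-sample, with noncentrality 0.75 / √(1/n₁ + 1/n₂):
- 16 versus 16: 0.75 / √0.125 = 2.12, 30 df, power about 54%.
- 20 versus 20: 0.75 / √0.1 = 2.37, 38 df, power about 64%.
- 8 versus 16 (one stimulation target, assuming an equal GPi/GPe split): 0.75 / √0.1875 = 1.73, 22 df, power about 38%.

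All three assume that d = 0.75, chosen for a rest-to-anesthesia change, also holds for a between-group difference in that change. The documents give no figure for the latter.

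**The case against.** **Almost certain false positives.** A reader might infer that false network findings are almost certain. The documents do not support that. They state neither the number of tests nor the number of bands. The measures come from the same signals and overlap, notably coherence, phase synchrony and phase lag index, so independence is the extreme case. At 50 tests and correlation 0.8 the chance of any false positive is about one in three. Every figure also assumes that all nulls are true. Nor do the documents show that chance results will be reported as findings.

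**Permutation testing.** A reader might also infer that everything outside MI is plainly uncorrected. Permutation critical values can control familywise error if they are built on a maximum or cluster statistic. The plan does not say that they are, and per-test permutation p-values do not do so. The fair description is that control is unspecified. Dynamic causal modelling selects among models and should not be counted as a set of p-values.

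**Exploratory purpose.** Aim 2 sets out to characterize signals, and the regression on clinical scores is worded as exploration. But section 1 calls these outcomes primary, and the sample size attaches power and alpha to them. The coupling analyses are not labelled exploratory.

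**Choice of primary.** Alpha/beta power is local spectral power, while Aim 2 is about networks. This is a fair reservation. A coupling measure could be named instead, but it would need its own effect size, which the documents do not give.

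**Conclusion.** The point stands. Neither aim has a specific primary measure, the only stated multiplicity rule concerns MI, and even there it follows a test of MI against surrogates and does not clearly reach contrasts of MI between conditions. Familywise error is uncontrolled and likely well above 5%. The illustration of 50 tests puts the chance of at least one false positive between about 32% and 92% for correlations from 0.8 down to 0, with 2.5 expected. This rests on one unadjusted 5% test per measure and pair and on all nulls being true; the true size cannot be fixed from the documents. The 16 patients suffice for one alpha/beta power test in Aim 2. They do not give 80% power for a comparison of Aim 3b with Aim 2 at the same d.

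**What to change.** 1. **Aim 2.** Name the patient-level change in average alpha/beta power from rest to the anesthetized state, at one prespecified recording site and time window, as the single primary outcome at two-sided 5%. State how the two bands are combined. This needs no extra patients.
2. **All other contrasts.** Within each aim, apply FDR at a stated level across every other measure × pair × band × state contrast, including between-condition contrasts of MI, and label them secondary or exploratory. If permutation critical values are meant to serve this purpose, state the maximum or cluster statistic and its family.
3. **Aim 3b.** Name one primary contrast on the same quantity, and say whether GPi and GPe stimulation are pooled or tested separately. If the contrast is stimulated versus the unstimulated Aim 2 patients, replace the one-sample 80% with the two-sample figure: about 54% at 16 versus 16 and 64% at 20 versus 20 for d = 0.75, and about 38% at 8 versus 16 if the targets are split equally and tested separately.

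**Cost.** Items 1 and 2 are changes of analysis wording, and fewer secondary connectivity results will reach significance. Item 3 is more than wording: the stated power for Aim 3b becomes less favourable, and the sponsor must accept that, enrol more patients or choose another contrast.
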